	improvement in TG/HDL ratio, improvement in insulin resistance, and >10%		
	improvement in ALT		
Study Duration (per	Up to 19 weeks total		
participant):	• Up to 6 weeks screening		
	12 week treatment		
Study Duration (calendar	• Study start-up: 0 – 4 months		
time):	Recruitment phase: 5 -14 months		
	Follow-up phase: 15 - 18 months		
Math Cale a duile :	Analysis and reporting: 18 - 24 months		
Visit Schedule:	Screening Visit		
	Baseline visit		
	Follow up visits		
Ctatistical Analysis	• Week 6 and Week 12 visits		
Statistical Analysis:	Descriptive variables of the cohort and subgroups will be analyzed using means and standard deviations or medians and ranges, as appropriate. Percent change in		
	primary and secondary outcomes will be compared using two sample t-test or		
	Mann-Whitney test. Absolute change over time will be compared using mixed		
	model or analysis of covariance.		
Sample Size:	A sample size of 11 participant per group is required to achieve a least 90% power		
Sample Size.	to detect a 15% point difference in the average % change in ALT from baseline to		
	week 12 between the two groups. Sample size was calculated assuming common		
	standard deviation of 10% using a two-sided Mann-Whitney tests with a 0.05		
	significance level. We will include 20 participants per group to allow for drop out,		
	intra-individual variability and multiple hypothesis testing.		
Safety Monitoring:	A DSMB will monitor the data for safety and efficacy for outcomes such as nausea,		
earcey monitoring.	abdominal pain, flatus, diarrhea, pregnancy, hepatotoxicity and any other outcomes		
	or events identified as safety related.		

Table of Contents

1.1 Primary Objectives71.2 Secondary Objectives72. Background & Significance73. Study Design113.1 Design Overview113.2 Inclusion Criteria113.3 Exclusion Criteria113.4 Rescreening123.5 Treatment Groups123.6 IMM-124E Administration123.7 Recruitment and Retention133.8 Sources and Materials133.9 Potential Risks133.10 Protection Against Risks143.11 Potential Benefits153.12 Data and Safety Monitoring164. Study Plan16
2. Background & Significance.73. Study Design.113.1 Design Overview.113.2 Inclusion Criteria.113.3 Exclusion Criteria.113.4 Rescreening.123.5 Treatment Groups.123.6 IMM-124E Administration.123.7 Recruitment and Retention.133.8 Sources and Materials.133.9 Potential Risks.133.10 Protection Against Risks.143.11 Potential Benefits.153.12 Data and Safety Monitoring.16

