7.1 Study Schedule of Events	
7.2 Blood Collection Schedule	

1. Objectives

We hypothesize that IMM-124E, a bovine colostrum enriched with anti-LPS antibodies, will improve insulin resistance and decrease systemic and hepatic inflammation through modulation of bacterial products and the microbiome in pediatric NAFLD.

1.1 Primary Objective: The principal objective of this blinded, placebo-controlled, pilot study is to evaluate whether 12 weeks of IMM-124E in children with NAFLD in combination with standard of care (SOC) will decrease inflammation in the liver as measured by ALT. Specifically, percent change in ALT from Week 0 to Week 12 in treatment compared to placebo.

1.2 Secondary Objectives:

- To assess the safety and tolerability of IMM-124E in children with NAFLD
- To assess the effects of IMM-124E on secondary and exploratory endpoints:
 - Mean change in ALT in treatment group compared to placebo
 - Fasting glucose and insulin
 - Hemoglobin A1C
 - o Adipo-IR
 - Oral glucose tolerance test
 - NAFLD pediatric diagnostic panel
 - Fasting plasma lipids
 - Stool microbiome
 - Blood transcriptomics
 - Systemic inflammation (cytokines)
 - Metabolomics
 - Visceral Adiposity (AMRA MRI scan)
 - Hepatic fat percent (AMRA MRI scan)
 - o BMI z-score
 - Waist circumference
 - Depression
 - Quality of life
 - Composite endpoint of "metabolic improvement" specified as > 10% improvement in TG/HDL ratio, improvement in insulin resistance, and >10% improvement in ALT

2. Background and Significance

Nonalcoholic fatty liver disease (NAFLD) is an aggressive, obesity-associated chronic liver disease that affects ~7 million children in the US (10% of all children) and is one of the top 3 indications for liver transplant in adults. Currently, the only treatment available for NAFLD is lifestyle advice to decrease adiposity and improve insulin sensitivity but this is rarely effective. It is our long term goal to improve the health of children by understanding how to prevent, treat and cure NAFLD. In our previous studies, we demonstrated that children with NAFLD have endotoxemia as well as systemic inflammation. Further, individuals with NAFLD have a disturbed microbiome (dysbiosis) and increased gut permeability. Thus, the mechanism of NAFLD is thought to include chronic inflammation from intestinal microbiome-derived

products (lipopolysaccharide (LPS) and metabolites) which pass through the "leaky gut" to the liver where they activate the innate immune response.

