3.4 Rescreening

If a potential participant fails screening due to a changeable criteria such as acute illness, use of a supplement or anti-oxidant, and ALT < $2 \times ULN$, the participant may rescreen a second time if they desire to after a reasonable amount of time has passed and if the investigator thinks the participant is likely to qualify the second time.

3.5 Treatment Groups:

Characteristics: 40 children age 6-19 years from any ethnic and racial categories will be included. Males and females will be recruited equally, however because of the increased prevalence of NAFLD in adolescent boys compared to girls, we may enroll more boys. In order for 40 children to complete the protocol, we will over-enroll at baseline by approximately 5 additional participants to allow for dropout.

NAFLD Patient Eligibility: Children ages 6-19 will be included because NAFLD typically presents around age 10, although sometimes at a young age. Young adults, age >19 years, will not be included because their travel for school and work makes participation more difficult. For NAFLD, each patient must meet the typical criteria for diagnosis including typical clinical and laboratory changes of NAFLD and liver biopsy or MRI consistent with NAFLD. If the subject only has had an ultrasound they may have their baseline MRI conducted up to 2 weeks prior to confirm the diagnosis. Subjects with 5% or more liver fat on their MRI will meet entry criteria and can proceed with the study. Other chronic liver disease must have been ruled out using a serologic work-up.

3.6 IMM-124-E Administration:

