5.2 Secondary Endpoints

Secondary efficacy-related outcomes will include change in: GGT, fasting glucose and insulin, total body insulin sensitivity (OGTT), BMI z-score, waist circumference, and quality of life. Safety-related outcomes will include: sex hormones, proportion of participants with nausea, emesis, diarrhea, and any other adverse event, PROMIS, body fat by MRI, hepatic fat by MRI, and change in metabolic state.

5.3 Power Analysis:

A typical group of patients with NAFLD have a mean ALT level of $130 \pm 63 \text{ U/L}^{10}$. In the TONIC treatment study of children with NAFLD, there was a -20 ± 10 U/L and -30 ± 8 U/L change (average of 15% – 23% change) in ALT in treatment groups respectively and no change in ALT with placebo at 12 weeks⁶. A sample size of 11 participant per group is required to achieve a least 90% power to detect a 15% point difference in the average % change in ALT from baseline to week 12 between the two groups. Sample size was calculated assuming common standard deviation of 10% using a two-sided Mann-Whitney tests with a 0.05 significance level.

5.4 Statistical Analysis:

Primary Outcome Analysis:

Change in ALT from baseline to week 12 will be converted to a % change from baseline to account for the wide range of ALT values expected at baseline. A Mann-Whitney U test will be used to compare the percentage change in ALT among the two intervention groups. Data will be described as mean or median percent change, as appropriate.

General Statistical Considerations:

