7.2 Attachment 2: Blood Collection Schedule (amounts in mL)

	Screening (-6 weeks)	Baseline (Week 0)	Week 6	Week 12	Total
Comprehensive Metabolic Panel	4	4	4	4	16
Serum	-	6	6	6	18
Plasma	-	12	6	12	30
Oral Glucose Tolerance Test					
(includes 4 mL 30 min serum tube)	-	9	-	9	18
PBMCs	8				8
Total	12	31	16	31	90

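### The primary ALT test has no baseline adjustment and leaves the screening ALT unused; a prespecified log-ALT ANCOVA with both pre-treatment values as covariates would use it

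*Combined protocol and SAP*

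**What the plan says.** Section 1.1 fixes the endpoint and its time points: "Specifically, percent change in ALT from Week 0 to Week 12 in treatment compared to placebo". Section 5.4, Primary Outcome Analysis, gives the derivation, "Change in ALT from baseline to week 12 will be converted to a % change from baseline", and the test: "A Mann-Whitney U test will be used to compare the percentage change in ALT among the two intervention groups". No covariate is named. The synopsis allows a t-test or Mann-Whitney for percent change, and neither of these adjusts for baseline. Analysis of covariance appears only for absolute change over time, which Section 5.4 assigns to secondary measures.

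A second pre-treatment ALT is available. Section 3.2 sets the entry threshold on ALT at screening (at least 46 for girls, 54 for boys). Section 4.1 places screening within six weeks of Week 0. Attachment 2 lists a "Comprehensive Metabolic Panel" of 4 mL at screening, Week 0, Week 6 and Week 12. No ALT threshold is stated for Week 0. Section 3.4 counts a low ALT among the changeable reasons for failing and allows a second attempt: "the participant may rescreen a second time if they desire to after a reasonable amount of time has passed".

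The synopsis gives dropout, "intra-individual variability and multiple hypothesis testing" as the reasons for taking 20 per group when 11 would meet the power target.

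**The concern.** A child's ALT varies from visit to visit. In a percent change from one Week 0 reading, the noise in that reading enters each child's result in full, and a rank test on the change cannot remove it. The synopsis names this variability as a reason to enrol more children, yet the analysis uses neither of the two inexpensive remedies: adjusting for baseline, and using the pre-treatment ALT already measured at screening.

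What is at stake is precision. Treatment is randomised and both arms pass through the same screening, so the planned comparison is not biased. But with 40 children and a result meant to inform a larger trial, lost precision makes an inconclusive answer more likely.

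**Working it through.** **1. The plan's own figure.** Inputs from Section 5.3: difference 15 points, SD 10%, two-sided 0.05, 90% power. Normal approximation: 2 × (1.960 + 1.282)² × (10/15)² = 9.3, so 10 per group. The two-sample t-test needs 10.40. Dividing by the Mann-Whitney efficiency 3/π (0.955) gives 10.89, so 11. Simulated Mann-Whitney power at 11 per group is 0.901. The stated 11 reproduces. On the same inputs, power at 20 per group is about 0.993, which leaves almost nothing to gain.

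**2. What an SD of 10% implies.** Section 5.3 gives ALT as 130 ± 63. If lognormal, the log-SD is √ln(1 + (63/130)²) = 0.46. Taking the SD of log change as about 0.10, 2(1 − r) × 0.46² = 0.01, so r is about 0.976 between Week 0 and Week 12. No within-child figure in the documents supports or refutes this. If the SD is larger (assumption), Mann-Whitney power for 15 points at 20 per group is 0.85 at SD 15%, 0.62 at 20% and 0.32 at 30%.

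**3. Variance left after each analysis.** Log scale, before selection, as a multiple of the variance at one visit; r is the Week 0 to Week 12 correlation.

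- Change from Week 0: 2(1 − r).
- ANCOVA on Week 0: 1 − r².
- ANCOVA on Week 0 and screening, all visit correlations equal: 1 − 2r²/(1 + r).
- Change from the average of the two, all correlations equal: 1.5(1 − r).

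| r | Change from Week 0 | ANCOVA, Week 0 | ANCOVA, both | Change from average |
|---|---|---|---|---|
| 0.6 | 0.80 | 0.64 | 0.55 | 0.60 |
| 0.7 | 0.60 | 0.51 | 0.42 | 0.45 |
| 0.8 | 0.40 | 0.36 | 0.29 | 0.30 |

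If correlation instead decays with time (first-order autoregressive, six-week gap), the screening value carries no information beyond Week 0. ANCOVA with both then stays at 1 − r² and loses one degree of freedom. Change from the average becomes 1 + (1 + √r)/2 − r − r√r, which is 0.82, 0.63 and 0.43: slightly worse than Week 0 alone.

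**4. Simulated power.** Assumptions: lognormal ALT with median 95 and log-SD 0.6 before selection, a single entry cut of 50, 20 per arm, and a true between-arm ratio of 0.75. The 25% is borrowed from Section 5.1. At least 2,500 runs per setting give a simulation error of about 1 point. The ranges show repeat runs.

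| Setting | r | Planned Mann-Whitney | ANCOVA, Week 0 | ANCOVA, both |
|---|---|---|---|---|
| Equal correlations | 0.6 | 35–37% | 45–46% | 47–49% |
| Equal correlations | 0.7 | 46% | 54–55% | 59% |
| Equal correlations | 0.8 | 62–63% | 70% | 76% |
| Decaying correlation | 0.6 | 36% | within about 1 point of both | 42% |
| Decaying correlation | 0.8 | 62% | within about 1 point of both | 66% |

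Type I error of the ANCOVA with both values was 4–5%. This model implies an SD of percent change of about 42–66%, far above the plan's 10%.

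**5. Smaller SDs and a 15% effect.** With visit CV 15% and no drift (SD of percent change about 22%), power is 0.63 for the planned test, 0.67 for ANCOVA on Week 0 and 0.77 with both values. With CV 10% and a six-week drift SD of 15%, the planned test has 0.484 and ANCOVA with both 0.496. With CV 5% and drift 20%, the figures are 0.376 and 0.371, so there is no gain.

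**6. Why not average.** With equal correlations, averaging moves the placebo median percent change from about +1 to between −3 and −5.5 points, because the screening value had to clear the threshold. Rescreening enlarges the shift. With an assumed population mean of 80 and CV 15%, placebo log change against the average is −0.9 points without rescreening and −1.2 with it, and about 0 against Week 0.

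**The case against.** Week 0 is a conventional baseline, stated consistently, and Mann-Whitney on percent change is a valid test. Nothing here is an error or a contradiction. Section 5.4 also says in general terms that covariates may be added where they could affect the response. On the plan's own SD, power at 20 per arm is about 99%, and the large gains appear only at SDs several times higher. All of this stands. The general covariate sentence does not specify an adjusted primary analysis, however, and the Mann-Whitney test as written cannot take covariates.

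A reader might infer more in three ways.

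- **That averaging screening and Week 0 ALT would cut regression to the mean and raise power at no cost.** The documents point the other way. The threshold applies at screening, so averaging puts the selected value into the baseline and makes within-arm falls look larger against the 25% benchmark of Section 5.1. Its power gain of 10–13 points at r 0.6–0.8 requires screening ALT to predict Week 12 as well as Week 0 does. With decaying correlation, power at r = 0.8 goes from 62% to 60%. Section 3.1 itself says that ALT can improve within several weeks.
- **That selection and rescreening bias the treatment comparison.** They act equally in both arms, so they do not.
- **That the unused screening value is a leading loss of precision.** In the favourable case, adjusting for Week 0 on the log scale contributes 7–9 points, more than the 3–6 from adding the screening value.

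**Conclusion.** The point holds as an improvement in efficiency, not as a flaw in validity. The planned primary test forgoes baseline adjustment and a second pre-treatment ALT that eligibility already requires. Replacing it with a log-ALT ANCOVA on both values raises simulated power by about 12–14 points if visit correlations are equal (35% to 47%, 62% to 76%) and by about 4–6 points if they decay (62% to 66%, 36% to 42%).

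These sizes rest on assumed lognormal ALT, a 25% between-arm reduction, 20 per arm, r of 0.6–0.8, and a screening panel that reports ALT. The gain is negligible if the SD of 10% is right, and it disappears if true ALT drift between visits dominates measurement noise. The documents do not allow a choice among these cases. The proposal still seems worth adopting, because the loss in the unfavourable settings examined was at most about 1 point.

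**What to change.** In Section 5.4, and in the matching synopsis text, make the primary comparison a prespecified ANCOVA of log Week 12 ALT on treatment, with log Week 0 ALT and log screening ALT as separate covariates. For rescreened children, name the qualifying screening value; a failed earlier value of undefined timing should not enter. Report the exponentiated treatment coefficient with its 95% confidence interval as the adjusted ratio of Week 12 ALT between arms. It reads as a percent difference and keeps the plan's aim of allowing for a wide baseline range.

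Keep Week 0 as the sole baseline for descriptive percent change and for the 25% benchmark in Section 5.1. Do not average the screening value into it.

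The cost is a few sentences settled before unblinding and one further degree of freedom for the screening covariate. No extra blood is needed, and eligibility already requires the screening value of every randomised child.

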3.9 Potential Risks

There is minimal risk in these studies. Potential risks are related to 1) blood draws, 2) NPO status, 3) cumulative blood loss 4) IMM-124E side effects and 5) confidentiality.

- The placement of an intravenous catheter and drawing of blood specimens has minimal risk of discomfort, bruising, or bleeding. There is minimal risk of infection or extravasation. Experienced staff with pediatric expertise will place all catheters and draw blood.
- 2) Patients will remain NPO from the midnight of the morning of the study until the fasting portion of the study is concluded. Fasting will be done before the Week 0 (Baseline) and Week 12 visits. Some children may become agitated with NPO status. Water will be encouraged to maintain hydration. Each participant will be asked to drink one glass of

water at bedtime prior to the study and one glass in the morning before leaving home for the research center.

- 3) Blood loss: To minimize risk to the patient, we will carefully monitor the total blood required for the 4 study visits and stay well within the NIH clinical center guidelines recommending less than 3ml/kg at a single research visit and no more than 7ml/kg over any 6 week period. See Table 2 for blood collection schedule and amounts.
- 4) Patients will be taking a concentrated milk protein product. It is possible that it could cause GI symptoms including nausea, diarrhea, gas, bloating or pain. Participants will be monitored for incidence and severity of gastrointestinal events.
- 5) There is risk of loss of confidentiality. Efforts will be made to keep all personal information confidential. All data will be stored in locked offices and password-protected computers. Personal identity will be protected in any publication.

Alternative treatments and procedures: New information on NAFLD diagnosis or new treatments for NAFLD in children may become available over the study period. This information will be incorporated into these studies and alternate diagnosis or treatment methods may be substituted if more appropriate. They will continue in the study if they desire and lab information from the study will be made available to their physician if requested.

3.10 Protection Against Risks:

Recruitment and Informed Consent

Recruitment will be through posted flyers and discussions of the study in the Children's subspecialty and general pediatric clinics and Health 4 Life clinic, by phone calls and letters to previous research participants who have previously consented to be contacted regarding future studies, letters to known NAFLD patients in the hospital medical record at Children's and through flyers and contacts at community pediatric offices and organizations.

Permission to perform this study will be sought from both the Emory University IRB and the Children's Healthcare of Atlanta IRB. Informed consent will be obtained from the parent or legal guardian and verbal or written assent will be obtained from the minor (depending on age). Informed consents and HIPAA waivers will be obtained by the parents or legal guardian prior to initiating any study procedure. Participants and their parents or legal guardian will be approached to participate in the study. The research coordinators and/or PI/Co-I will discuss the study with them and give them all the information listed above in language understandable at the level of the parent/guardian and all information needed to make an informed choice about participation, including information about NAFLD, the study medication, possible side effects, IMM-124E, study procedures, study visits/contacts and potential benefits to the participant. Consent will be documented by signature of the parent/guardian. Oral consent will be obtained for 6-10 year old participants. Written assent will be documented by signature in age 11-17 year old participants and written consent in 18 and 19 year old participants. Verbal consent will be used for fasting procedures and 24-hour recalls. The screening visit requires that the patient is

fasting at the time of the blood draw. Verbal consent will be used to document that the participant agrees to fast and possibly answer questions about their diet over the phone before coming in for their first visit where they will then sign the informed consent document. They will be made aware of the risks of fasting during this discussion.

Other Protections Against Risk

Risk will be minimized to the children by using nurses and research coordinators experienced in pediatrics for the research studies. Risk to confidentiality will be reduced by using non identifying participant numbers and removing all identifiers as early as feasible. Only study personnel will have access to identifying data. Laboratory personnel will only have access to numeric identifiers and the key will be kept in a password protected database.

Additional protection for children: all children must provide verbal and written assent or consent. In our studies, we allow children to decline to continue to participate at any time before and during a study or study visit. During study visits, if blood cannot be drawn and the child does not wish to have it attempted again, we encourage them to tell us this and we assess willingness to complete other study procedures not requiring venipuncture. Study stipends are provided at a standardized pro-rated level appropriate for the time/study procedures completed.

Side effects of IMM-124E will be monitored and tracked carefully. We will report Serious, Unexpected Suspected Adverse Reactions (SUSAR) to the FDA, and IRB within 15 calendar days after determining reportability. Any unexpected fatal or life threatening suspected adverse reaction will be reported within 7 calendar days of initially receiving information on the event. Unanticipated problems (UPs) are reportable to the IRB within 10 days according to IRB policy. Serious adverse events or SUSARs that are not UPs and for which there is a reasonable possibility that the drug and/or research procedures caused the event or reaction are reportable to the IRB at continuing review.

3.11 Potential Benefits:

Potential Benefits to Participants:

The proposed research has substantial potential benefits for children but may not benefit the individual participant. All children will receive standard of care. The establishment of a drug that is safe and has high efficacy in treating NAFLD in children will allow for prevention of secondary diseases associated with NAFLD as well as improved quality of life in the affected children.

Participants in the study will receive copies of their liver transaminases results and these will be discussed with them at the end of the study. Education will be provided as appropriate regarding the results. At the conclusion of the study, participants will meet with a member of the study team and the families will be provided important long term healthy diet and physical activity education as well as information for the parent on methods to prevent/reduce childhood obesity.

Importance of Knowledge to be Gained:

NAFLD is the most common liver disease in children today and the prevalence of the disease has more than doubled over the past 2 decades to include > 7 million children in the US. Liver disease is more

common among Hispanics and is responsible for increased morbidity and mortality. NAFLD is a contributor to this health disparity. There is evidence to suggest that once a child has NAFLD, it may be difficult to completely reverse. Further, there is substantial evidence to show that NAFLD is a key event in the global dysmetabolism of the metabolic syndrome and acquiring NAFLD predicts future morbidity and mortality from type II diabetes, strokes, heart attacks, cirrhosis and liver cancer. It is critical to develop prevention and treatment for NAFLD. At this time, it is not known when NAFLD typically starts and standard of care is to test all obese children periodically starting at age 10 to see if and when they have developed NAFLD. This study may provide data to inform clinical practice regarding younger children in high-risk groups. This study will improve patient care, provide potential treatment, support public health policy regarding NAFLD, and decrease health disparity in the affected children.

3.12 Data and Safety Monitoring:

Data Management: Data for each participant will be collected in individual folders kept in a secure filing cabinet in the offices of the Division of Pediatric Gastroenterology/Hepatology/Nutrition. Data will be entered into a secure database in the same division.

Adverse Events: The principal investigator will monitor side effects and unexpected occurrences through the course of the study. Side effects of IMM-124E will to be monitored closely.

A status report will be provided to the Institutional Review Board of Emory University at the time of continuing review. In the event of a serious and unexpected adverse event, the A-CTSI, and the NIH program officer will be notified within 3 working days of the event. The Emory and Children's IRBs will be notified according to IRB policies & procedures.

The PI will determine if any of these events which occur, is due to the study medication or study procedure or is an expected event given the disease state of the participants. The PI is an experienced pediatric hepatologist and pediatrician and will be responsible for determining serious adverse events (SAE) and whether or not they are due to the study medication.

A SAE will be reported to the DSMB within 2 days of occurrence. The DSMB will review all potential SAEs to make the final decision.

Data and Safety Monitoring Board: Medical monitoring will also be provided by the DSMB by Emory faculty who are not involved with this study. All SAE will be reported to the DSMB within 2 days of the occurrence and all side effects recorded will be reported at the end of the study to allow independent assessment of the likelihood of them being from the study mediation.

The DSMB will meet bi-annually to review progress, SAEs, and outcome data.

4. Study Plan

This study will be conducted in accordance with current US FDA regulations and guidelines, ICH guidelines on GCP, as well as all other applicable research regulations set forth by Emory University and Children's Healthcare of Atlanta. Informed consent and assent will be obtained for this study by the principal investigator or her designees from all study participants prior to any protocol-specific procedures are performed.

4.1 Screening and baseline data collection:

Candidates who appear eligible will be screened by reviewing their medical records to determine whether they meet the eligibility criteria. Physicians of eligible candidates will be contacted and the patients may be visited in clinic by the study coordinator directly.

Subjects may be approached by the research team about the study either in person in clinic or over the telephone. A verbal consent will be obtained at this time if the subject is interested in scheduling a screening visit. The patient will be instructed to not have anything to eat or drink (except plenty of water) for 12 hours prior to the scheduled research visit. They will also be made aware of the risks associated with fasting (feeling lightheaded or agitated). If the screening window is anticipated to be shorter than usual (based upon the patients schedule etc) then the study team may need to collect a 24-hour dietary recall during the screening period prior to the initial screening visit (where the patient first signs the informed consent document). This procedure is also detailed in the verbal consent. A member of the study team will call the subject on the telephone and will ask them what they have had to eat and drink in the last 24 hours.

If the patient is approached about the study in clinic and chooses to screen during their appointment then the verbal consent will not be required if the subject is already fasting for intended SOC labs.

Participants who sign consent/assent documents will be registered in study and assigned a study number. If the participant does not meet eligibility criteria or meets all the eligibility but decides not to continue in the study before randomization at Week 0 he or she will be deemed a screen failure. A screening log will be kept to track all screening activities and reasons for screen failures. As described above, a patient may be screened a second time if they desire this and the reason for failure is likely to have resolved in the opinion of the investigator.

Screening procedures will be performed as indicated in the Study Schedule of Events (Attachment 1). Recording of any patient information will not begin until informed consent and assent has been obtained. The screening visit will take place within six weeks of the randomization date, Week 0.

Screening visit (up to - 6 weeks)

Pre-screening activities such as chart review of standard of care labs or referral from a colleague will identify potential participants for screening. If the participant is deemed eligible he or she along with a legal guardian will sign the consent/assent documents before or during the screening visit.

After informed consent is obtained the following procedures will be conducted at the screening visit:

- Review inclusion and exclusion criteria
- Collection of demographics
- Collection of vitals (including blood pressure, respiratory rate, heart rate, and body temperature)
- Anthropometric assessments (including height, weight, waist and hip circumference)
- Medical history review
- Review of concomitant medications
- Administration of 3, 24-hour recalls (NDS-R) during the screening period
- Administration of the Alcohol Use Disorders Identification Test (AUDIT)
- laboratory assessments (see Blood Collection Schedule Attachment 2 for more detail)
- If the subject has had an ultrasound, but not an MRI or liver biopsy prior to screening:
 - The Baseline MRI will be conducted prior to the baseline visit. If the liver fat from this MRI is great or equal to 5% then the subject may continue in the study. These subjects will have their Baseline visit within 2 weeks of the MRI.

Baseline Visit (Week 0):

In order for a participant to be randomized all screening procedures must be completed and participants must meet all inclusion and meet no exclusion criteria prior to randomization. The randomization visit will take place up to 6 weeks after the screening visit.

All participants will be randomized at Week 0 to receive one of two arms of therapy (drug or placebo). All participants will receive a supply of study drug/placebo at Week 0. These bottles will be issued to the patient by the research pharmacist based on the randomization assignment generated at the Week 0 visit.

The following procedures will be conducted at the randomization visit:

- Reaffirmation of consent
- Physical Examination
- Concomitant medication and adverse event review
- Confirmation that participant is feeling well
- PROMIS Questionnaires (patient reported outcomes)
- Collection of vitals (including blood pressure, respiratory rate, heart rate, and body temperature)
- Anthropometric assessments (including height, weight, waist and hip circumference)
- Education on drug administration and adverse effects monitoring
- 2-hour oral glucose tolerance test
- Standardized education on an appropriate diet (participant-specific) and living a healthy lifestyle:
 - A goal of 60 minutes of exercise every day
 - Reduce sugar-sweetened beverage intake
 - Increase vegetable intake
 - Reduced carbohydrate intake
- Drug dispensing and instruction from research pharmacy
- Fasting laboratory assessments (see Blood Collection Schedule Attachment 2 for more detail)
- Stool sample collection
- Urine pregnancy test for females of childbearing potential
- Blood spot collection
- MRI (Brief scan for full body and liver fat assessment)

• Optional Sub-study: Accelerometer data collection for 1 week

4.2 Randomization Procedures:

After consent and eligibility for the trial is confirmed, participants will be randomly assigned to either IMM-124E or placebo. The randomization will be assigned by the research pharmacist and will be blocked by age group (6-12 years versus 13-19 years) to ensure balanced groups. The investigators, lab personnel, research coordinators and participants will be blinded to the assignment. The research pharmacy will dispense the similarly appearing IMM-124E and placebo at baseline and again at Week 6.

